7.8. Causality

For all adverse events, the investigator must pursue and obtain adequate information to determine the outcome of the adverse event and to assess whether the AE meets the criteria for classification as an SAE, serious suspected adverse reaction, suspected adverse reaction, unexpected adverse event, or unexpected suspected adverse reaction. For all adverse events, sufficient information should be obtained by the investigator to determine the causality of the adverse event. For adverse events with a causal relationship to the IP or the enema procedure, follow-up by the investigator is required until the event or its sequelae resolve or stabilize at a level acceptable to the investigator.

The Investigator will make a causality assessment for all AEs and decide whether there is a reasonable possibility that the AE may have been caused by the study product or procedure, including an assessment of biologic plausibility, presence or absence of alternative causal explanations (such as continuation or exacerbation of the subject's recurrent CDI symptoms), and temporal relationship to product administration and/or the procedure. Relatedness to RBX2660 or the enema procedure is defined as:

Unrelated: The event is due to an underlying or concurrent illness or effect of concomitant therapy and is not related to the study product or procedure (e.g., has no temporal relationship to study product or procedure, or has a much more likely alternative etiology)

Possible: There is some temporal relationship between the event and the administration of the study product or procedure, though the event could also be explained by the subject's medical condition or other therapies.

Probable: The temporal relationship between the event and administration of the study product or procedure is suggestive, and the event is unlikely to be explained by the subjects' medical condition or other therapies alone.

Definite: The event follows a reasonable temporal sequence from administration of the study product or procedure, follows a known or suspected response pattern to the study product and/or procedure, improves upon stopping the study product, and reappears upon repeated exposure, if that occurs.

If an investigator is unsure about whether to report a finding as an adverse event, s/he is encouraged to enter the finding as an AE into the study database.

7.9. Pregnancy Reporting

If the subject or partner of a subject participating in the study becomes pregnant during the study after IP administration, the investigator should report the pregnancy to Medpace Clinical Safety within 24 hours of being notified. Medpace Clinical Safety will then forward the Exposure In Utero form to the investigator for completion.

The subject or partner should be followed by the investigator until completion of the pregnancy. If the pregnancy ends for any reason before the anticipated date, the investigator should notify Medpace Clinical Safety. At the completion of the pregnancy, the investigator will document the outcome of the pregnancy. If the outcome of the pregnancy meets the criteria for immediate classification as an SAE (i.e., postpartum complication, spontaneous abortion, stillbirth, neonatal death, or congenital anomaly), the investigator should follow the procedures for reporting an SAE.

7.10. Medical Monitor

An independent Medical Monitor reviews all serious adverse events and other events reported by the site as related to the investigational product or enema procedure to provide an objective, qualified judgment of the events. The Medical Monitor is a physician not participating as an investigator in this study. The Medical Monitor has the responsibility to review and evaluate the information relevant to product safety throughout the development and implementation of the protocol. The Medical Monitor will remain blinded throughout the study. The Medical Monitor performs the following functions:

- Reviews SAEs and other adverse events as requested;
- Reviews the study protocol and Investigator's Brochure for adequacy of safety oversight;
- Confers with site investigators, DSMB and the Rebiotix Clinical Department as applicable regarding potential safety concerns;
- Provides medical surveillance and provides appropriate recommendations for the conduct of the study as needed.

Details of the Medical monitor activities and expectations will be documented in a Safety Management Plan.

7.11. Data and Safety Monitoring Board (DSMB)

The DSMB consists of three physicians specializing in infectious diseases or gastroenterology who have experience managing subjects with recurrent CDI and are not investigators in the study. A biostatistician who is not involved with study design or analyses may assist the DSMB. The DSMB will operate in accordance with applicable sections of the FDA Guidance for Clinical Trial Sponsors *Establishment and Operation of Clinical Trial Data Monitoring Committees*.

Details of the DSMB logistics, activity and responsibilities will be included in a DSMB charter. General responsibilities include oversight of subject safety through data review and assessment of trends. This includes the ability to stop the study based on pre-defined stopping rules. Additionally, the DSMB will provide an independent review of the efficacy data to ensure the benefits of providing this treatment to subjects outweighs the risks.

7.12. Study Stopping Rules for Safety

Medpace Safety personnel or designee will review all adverse events reported during the study to observe for trends and unanticipated events, either in severity, seriousness or incidence, and to assess if a study stopping rule may be triggered. Adverse event review includes the event description, onset date in relation to the treatment date, and the investigator's determination of causal relatedness to IP, the enema procedure, and pre-existing condition, as well as rating the event's severity and seriousness. Additionally, the Medical Monitor assessment of seriousness and causality will be provided and reviewed as it may be different from the site investigator report of the event. If necessary, the DSMB may be unblinded to adjudicate specific adverse events as per the study stopping rules, below. Anticipated AEs may trigger the study stopping rules.

The DSMB will determine whether enrollment should be paused, the study terminated, or other actions taken based on their assessment that:

- a) There is probable cause that IP or enema procedure (e.g., due to transfer from an RBX2660 donor) contributed to a pathogenic intestinal infection in the stool of any subject, or
- b) Any series of events of major significance such as death or other serious outcome for which a causal connection with the IP is plausible represents an excess of the important adverse event(s) in one of the study arms.

To support the DSMB assessment, the Rebiotix Operations Department may be asked to review the donor history and batch processing/release records for the product unit(s) administered in these cases, and forward its report to the DSMB Chair for review. The DSMB Chair will review the Operations Department report and may be unblinded to the

randomization assignment. If probable cause is suspected, the DSMB Chair will convene the entire DSMB for event review.

Upon the DSMB's determination of action, the Chair will notify the Rebiotix Clinical Department, who will notify the study sites.

If enrollment is stopped, Rebiotix and the study sites will assess for the occurrence of similar events, and evaluate IP and study records for possible root cause(s). Enrollment may be re-started upon further review and approval from the DSMB. As appropriate, the DSMB may recommend study termination or measures short of termination with the objective of reducing the risk of adverse events.

7.13. Sponsor Reporting of Adverse Events

The sponsor will report all relevant information about suspected unexpected serious adverse reactions that are fatal or life-threatening as soon as possible to the FDA & Health Canada, and in any case no later than seven days after knowledge by the sponsor of such a case, and that relevant follow-up information will subsequently be communicated within an additional eight days.

All other suspected unexpected serious adverse reactions will be reported to the FDA as soon as possible but within a maximum of 15 days of first knowledge by the sponsor.

The sponsor will also inform all investigators as required.

7.13.1. Timeline for Reporting Requirements

The following describes the expedited safety reporting requirements by timeline for reporting and associated type of event:

- **Within 7 calendar days of event discovery by Rebiotix**
Rebiotix will notify FDA and Health Canada of any unexpected fatal or life-threatening suspected adverse reaction as soon as possible but in no case later than seven calendar days after the sponsor's initial receipt of the information.
- **Within 15 calendar days of event discovery by Rebiotix**
The AE must meet all three of these criteria for expedited reporting.
Any study event that is:
 - suspected adverse reaction
 - serious
 - unexpected

7.13.2. Additional Reporting Requirements

The sponsor will identify in IND safety reports all previous reports concerning similar adverse events and analyze the significance of the current event in light of the previous reports.

7.13.3. Reporting AEs to FDA and Health Canada

Rebiotix will report adverse events to FDA and Health Canada as required by applicable regulations. All adverse events will be reported in the annual and final clinical study reports.

8. Sample Size and Statistical Considerations

This study has a Statistical Analysis Plan which contains complete details of the statistical methodology and analyses that will be employed for this study.

8.1. Assessment of Efficacy

The primary efficacy parameter is treatment success, defined as the absence of CDI diarrhea through 8 weeks after completing a study treatment. Efficacy assessments will occur at the 1-, 4- and 8-week office visits.

Recurrence of CDI after 8 weeks from completion of the assigned study treatment is considered a new *C. difficile* infection, as defined by the Centers for Disease Control (CDC website http://www.cdc.gov/hai/eip/cdiff_techinfo.html; published August 30, 2012; accessed October 02, 2016).

Primary Efficacy Endpoint: Recurrence of CDI within 8 weeks of blinded treatment.

The primary efficacy analysis will be performed on all pre-defined analysis populations comparing the RBX2660 arm to the Placebo arm, Intent-to-Treat (ITT), modified Intent-to-Treat (mITT) and Per-Protocol (PP). However, the determination of meeting the pre-defined primary efficacy endpoint will utilize the mITT population results. The primary analysis of the study will be a Bayesian hierarchical model, which formally incorporates data from a previous randomized Phase 2b study (Protocol 2014-01) of RBX2660. This analysis will demonstrate the efficacy of RBX2660 by showing a sufficiently high posterior probability that the rate of success in the treatment group is superior to the rate of success in the control group. Secondary efficacy endpoints will also be completed on all analysis populations. Finally, all safety analyses will be performed on the Safety

population (SP) which includes all subjects in whom a blinded enema was at least opened and attempted.

A primary efficacy and safety analysis for primary efficacy and safety will be conducted when 100% of the applicable subjects in each group have completed their 8-week follow-up assessment after receiving the blinded treatment. Safety analysis will be completed for safety endpoints defined at or prior to 8 weeks following blinded treatment along with any longer term safety data available at the time of analysis. The analyses will be submitted to FDA for review. One or more interim analyses will be conducted to evaluate the primary efficacy endpoint for possible early study stopping for success or futility. The first interim analysis will occur after a minimum of 160 subjects have been treated and evaluated for efficacy. A second interim analysis could occur when 220 subjects have been treated and evaluated for efficacy if success is not achieved at the first interim analysis. The details of the planned interim analyses are included in the statistical analysis plan.

Final long-term safety results as well as unblinded RBX2660 efficacy data will be analyzed and reported in a final report after the last subject has completed the 6-month follow-up visit for their study treatment. This includes 6-month follow-up after an unblinded RBX2660 study treatment. At that time the study will be considered complete.

To demonstrate a 69% success with one dose of the RBX2660 treatment group vs. 47% success in the Placebo control group in a 2:1 randomization ratio, 240 subjects are required (power $\geq 90\%$ with a nominal 2.5% type I error rate). Up to an additional 30 subjects will be enrolled to allow for a 10% loss-to-follow up rate, for a total of up to 270 subjects. Considering the 2:1 randomization, this results in approximately 180 subjects in the RBX2660 arm and 90 subjects in the Placebo arm. Potential subjects who have signed consent but do not meet all inclusion and/or exclusion criteria will be considered screen failures. Randomized subjects who withdraw for any reason prior to administration of the blinded enema will be replaced without counting toward the sample size cap which may result in more than 270 subjects being randomized, however no more than 270 subjects will be treated with a blinded enema. Replacement subjects will also be randomized to ensure proper blinding.

Subjects who are exited prior to randomization or randomized but exited prior to treatment may be re-enrolled and thus randomized under different subject identification numbers (re-randomized). If this occurs, they will be included in the analysis using their second randomization assignment and subsequent assessments only and will only be counted once towards the total randomized.

9. Study Administration

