6.11. Telephone Assessments (Weeks 2, 3 and 6)

Qualified and trained site staff, as recorded on the Delegation of Authority Log, make the phone calls and may follow the script provided. All data collected are to be recorded and reported as required in Section 6.15. These phone calls must occur within the window specified in Table 6-1; phone calls out of window or missed phone calls are to be reported as protocol deviations.

The following study activities/data will be collected at the telephone assessment calls:

- Assess recurrence of CDI
- Adverse event collection, including new onsets of obesity, metabolic syndrome, pre-diabetes, diabetes and/or autoimmune disorders
- Changes to concomitant medications since the last visit
- Assess for protocol deviations

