6.2 Time Point Algorithms

6.2.1 Relative Day

The date of study enema administration will be considered relative day 1, and the day before study enema administration will be relative day -1. Relative days will be calculated as follows only when the full assessment date is known (i.e., partial dates will have missing relative days, unless imputation methods have been specified):

For days before first enema:

Date of Assessment – Date of first enema administration

For days on or after first enema:

Date of Assessment – Date of first enema administration +1

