6.2.2 Windows

For the purpose of statistical analysis, the analysis visit windows will be calculated in terms of study days since the day of the study enema administration, as illustrated in the following tables:

Analysis Windows for Clinical Visits

Visit	Scheduled Study Day	Visit Window in Protocol (Days)	Visit Window for Analysis (Days)
Screening Visit	-30 through -1	-30 through -1	-30 through -10
Baseline/1 st Enema	1	1	1
Week 1 Office	8	5 - 11	5 - 11
Week 4 Office	29	26 - 32	26 - 32
Week 8 Office	57	54 - 60	54 - 60

Analysis Windows for Phone Assessments

Visit	Scheduled Study Day	Visit Window in Protocol (Days)	Visit Window for Analysis (Days)
Week 2 - Phone	15	12 - 18	12 - 18
Week 3 - Phone	22	19 - 25	19 - 25
Week 6 - Phone	43	40 - 46	40 - 46
3 month - Phone	90	76 - 104	76 - 104
6 month - Phone	180	166 - 194	166 - 194

If a subject has more than one assessment occurring in the same visit window, the data from the visit closest to the scheduled study day will be used for analysis. If two visits have the same distance from the scheduled study day, i.e., one visit occurs -1 day from study day, and the other visit occurs +1 day from study day, the data from the visit after the scheduled study day will be used for analysis.

Analysis Windows for Adverse Event Reporting by Onset Interval

Onset Interval Name	Onset Interval Analysis Window	Window for Analysis (Days)
Baseline	Screening - < Baseline	≤ -1
1-week	Baseline - 1-week	1 through 8
4-week	> 1-week - 4-week	9 through 29
8-week	> 4-week - 8-week	30 through 57
4-month	> 8-week - 4-month	58 through 121
6-month	> 4-month - 6-month	122 through 180+

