An analysis of time to CDI recurrence after completion of the assigned blinded treatment will be analyzed and presented by the Kaplan-Meier procedure and median duration presented by days (and weeks) using the ITT, mITT, and PP populations. The Kaplan-Meier estimate of the median time (days) and the associated 95% confidence interval will be presented for each treatment group. A graphic presentation of the Kaplan-Meier estimates will supplement the tabular presentation. Between group comparisons will be performed using the stratified log-rank test based on the stratification factor at randomization. The corresponding hazard ratio of the treatment effect along with the 95% confidence interval will be calculated using a Cox proportional hazard model with treatment and the stratification factor at randomization as explanatory variables.

Time to CDI recurrence is defined as the number of days from enema administration to first assessment indicating recurrence for those subjects who were deemed Treatment Failures with CDI recurrence. All subjects who are Indeterminate or discontinued for any reason prior to assessment of efficacy will be censored at the last assessment date at/prior to Week 8. For the analysis of Time to CDI recurrence within 8 weeks, all subjects considered as a treatment success will be censored at the date of their 8-week assessment. For the analysis of Time to CDI

recurrence through 6 months, all subjects considered to have achieved sustained clinical response will be censored at the date of their 6-month assessment.

Finally, the sensitivity of the primary efficacy endpoint will be assessed in a multivariate logistic regression adjusting for possible interactions of the following covariates with treatment group: age (< 65 years, \geq 65 years), sex (Female, Male), race group (White, Non-white), ethnicity (Hispanic-Latino, not Hispanic-Latino), site geography (outside the US, Eastern US*, Southern US*, Northern US*, Western US*), randomization strata (i.e., treatment received at the qualifying event) and number of previous episodes of CDI recurrence at baseline. Other baseline variables will be compared for balance using the appropriate statistical test. This analysis will be performed on all analysis populations where at least 20 subjects in each sub-group are available for analysis to fully understand the observed treatment effect.

*States included in the identified US geographical regions are as follows:

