Time to CDI occurrence is defined as the number of days from enema administration to first assessment indicating recurrence, for those subjects who were deemed Treatment Failures or Indeterminate. Randomized subjects who do not complete the assigned blinded treatment will be censored at Day 0. All subjects who are discontinued for any reason prior to the 6-month timepoint will be censored at the last assessment date at/prior to Month 6. All subjects considered as a sustained treatment success will be censored at the date of their 6-month assessment.

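### Dating CDI events at the detecting assessment and censoring each success at its own visit makes the tail of the supportive Kaplan-Meier curves depart from the crude success rate

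*Protocol*

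**What the plan says.** **Event time.** SAP 7.6.1.2: "Time to CDI recurrence is defined as the number of days from enema administration to first assessment indicating recurrence". SAP 7.6.2.1 uses the same rule for the 6-month analysis: "Time to CDI occurrence is defined as the number of days from enema administration to first assessment indicating recurrence".

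**Censoring.** In the 8-week analysis, "all subjects considered as a treatment success will be censored at the date of their 8-week assessment". In the 6-month analysis, "All subjects considered as a sustained treatment success will be censored at the date of their 6-month assessment".

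**Visit windows.** SAP 6.2.1 numbers the enema day as day 1, so 8 weeks (56 days) is study day 57. SAP 6.2.2 lets the week-8 visit fall on study days 54 to 60 ("Week 8 Office 57 54 - 60 54 - 60") and the 6-month call on days 166 to 194, around day 180.

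**When recurrence can be found.** Protocol 8.1 says "Efficacy assessments will occur at the 1-, 4- and 8-week office visits". That list is incomplete. The week 2, 3 and 6 calls in Protocol 6.11 also include "Assess recurrence of CDI", and Protocol 6.13 requires an unscheduled visit whenever recurrence is suspected within 8 weeks.

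**Reading day.** SAP 7.6.2.1 presents estimates at the scheduled assessment times. SAP 7.6.1.2 names no day for reading the 8-week curve. It asks for a Kaplan-Meier figure and a median with a 95% interval per arm.

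**The concern.** The endpoint in Protocol 3.7 is CDI diarrhea within 8 weeks of the enema. The time-to-event analyses use the date of detection instead, and no common cut-off day is set.

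Within days 54 to 60 a success leaves the risk set because a visit took place and was negative, while a failure found at such a visit is an event. Exit time and outcome are therefore tied together. Each failure found late in the window is divided by the few subjects not yet seen, and the curve drops too steeply. With complete follow-up, Kaplan-Meier should reproduce the crude proportion; under this rule it generally does not.

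At stake is a figure and a table offered in support of the primary result. They could show a different success rate from the adjudicated proportion in the same subjects. The placebo median is exposed because assumed placebo success (47%) lies close to 50%.

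**Working it through.** **1. The plan's own figure.** SAP 6.4.2 gives 99.5% log-rank power with 104 per group and exponential event times from 8-week success of 69% and 47%. The daily rates are -ln(0.69)/56 = 0.00663 and -ln(0.47)/56 = 0.01348, a hazard ratio of 0.491. Simulating 10,000 trials at two-sided 0.05 gives 99.6%, so the plan's figure is reproduced and the same rates serve below.

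**2. Closed form for the 8-week curve.** Let p be true 8-week success and s the share of failures first found at the week-8 visit. The documents do not give s; it is assumed to be 10%, with a range of 5% to 20%. Visits are assumed uniform over the seven days.

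- Share still at risk when the window opens: A = p + s(1 - p).
- Fraction of these who fail at the visit: f = s(1 - p)/A.
- On the successive days 54 to 60 the curve is multiplied by (1 - f/7), (1 - f/6), ..., (1 - f/1).

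At s = 10%:

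- RBX2660: A = 0.69 + 0.031 = 0.721; f = 0.031/0.721 = 0.0430.
- Placebo: A = 0.47 + 0.053 = 0.523; f = 0.053/0.523 = 0.1013.
- Day 57 (first four factors): 0.698 and 0.484.
- Day 60 (all seven factors): 0.644 and 0.399.

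Results (RBX2660 / placebo) against the true 0.69 / 0.47, difference 22 points:

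| s | Day 57 | Diff. | Day 58 | Day 60 | Diff. |
|---|---|---|---|---|---|
| 5% | 0.694 / 0.477 | 21.7 | 0.689 / 0.468 | 0.666 / 0.431 | 23.5 |
| 10% | 0.698 / 0.484 | 21.4 | 0.688 / 0.468 | 0.644 / 0.399 | 24.5 |
| 20% | 0.706 / 0.500 | 20.6 | 0.687 / 0.469 | 0.604 / 0.347 | 25.7 |

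The curve is slightly high at day 57, crosses the true value at about day 58, and is low at day 60.

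**3. Dependence on how failures are found.** These are simulations with 600,000 subjects per arm, exponential onset and uniform visits:

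| Detection | Day 57 | Day 60 |
|---|---|---|
| Office visits only | 0.737 / 0.547 | 0.522 / 0.276 |
| Office visits and calls | 0.717 / 0.510 | 0.597 / 0.355 |
| 80% at unscheduled visits, 2 to 5 days after onset | 0.700 / 0.485 | 0.643 / 0.410 |

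If onset is strongly front-loaded (mean 14 to 21 days) and every failure is found 2 to 5 days after onset, the bias is 0.2 to 0.9 points. With milder front-loading (Weibull shape 0.7), visits clustered in the window and every failure found within 1 to 2 days, the end of the curve is 0.669 / 0.443, about 2 to 3 points low.

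**4. Medians.** At s = 10% the placebo curve enters the window at 0.523 and passes 0.5 on day 56 (0.4965). At s = 20% it does so on day 57 (0.4996). The exponential onset median is ln 2/0.01348 = 51.4 days after the enema. With 180/90 subjects and visits clustered around day 57, the RBX2660 curve reached a median in 9% of simulated trials at s = 10% and 20% at s = 20%, although true success is 69%.

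**5. Tests.** In simulations at 180:90, 8-week log-rank power under the SAP rule, against onset dating with a day-57 cut, was 92.6% against 94.9% (office only), 93.6% against 94.4% (office and calls) and 94.4% against 94.6% (80% unscheduled). Type I error was 4.6% to 5.4% under either rule.

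**6. Six months.** Week-8 successes stay at risk here, so nothing shrinks on days 54 to 60. Protocol 1.5.2 gives 91/95 free of CDI long term, so late CDI is 4/95 = 4.2%. If late CDI is found only at the 3- and 6-month calls, RBX2660 reads 0.669 at day 180 and 0.604 at day 194, against a true 0.662. At an assumed 20% late CDI the figures are 0.591 and 0.348 against 0.552.

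**The case against.** A reader might infer that Kaplan-Meier success always falls below the truth and that the rule flatters RBX2660 by widening the arm difference. The documents do not support that. Eight weeks is study day 57, and there the curve is at or slightly above the true rate and the difference slightly narrower. Only the last days of the window show a deficit and a wider difference. Log-rank power is slightly lower, which is no gain for the drug.

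The share of failures found at week 8 is also an assumption, and the protocol works against a large one. Protocol 6.7 asks subjects to call if symptoms recur, 6.11 adds telephone checks, and 6.13 requires a visit on suspicion. The toxin test must be positive while diarrhea is present, so a failure first found at week 8 normally has diarrhea at that time.

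Dating at a confirmed assessment is defensible in itself. The post-enema diary ends at the 1-week visit (Protocol 6.3), and no section confirms that an onset date is recorded. Finally, SAP 7.6.2.1 reads the 6-month curve at scheduled times, where the distortion is small.

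These points stand and limit the concern. They do not remove it: SAP 7.6.1.2 names no reading day, asks for a figure and medians, and links exit time to outcome within the window.

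**Conclusion.** The concern holds in a limited form. As written, the 8-week Kaplan-Meier curve need not equal the crude success rate even with complete follow-up. With 10% of failures found at the week-8 visit and uniform visits, it is about 1 point high at day 57, and about 5 points (RBX2660) and 7 points (placebo) low at day 60. These sizes rest on the assumed share, visit spread and onset pattern, and prompt detection shrinks them. The 6-month analysis has the analogous effect only at days 166 to 194, and it is small at day 180 when late CDI is rare.

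The effect is confined to supportive curves, estimates and medians, and to a loss of at most about 2 points of 8-week log-rank power. It would be wrong to infer that the trial's conclusion is at risk: the Bayesian primary analysis uses adjudicated counts, and the chi-square tests of 8-week success and of sustained response use proportions. Severity: minor.

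**What to change.** In SAP 7.6.1.2 and 7.6.2.1:

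1. Date an adjudicated failure at the first day of the qualifying diarrhea where recorded, otherwise at the detecting assessment.
2. Cap the event time of any adjudicated 8-week failure at study day 57, and of any 6-month event at study day 180.
3. Censor all successes at the same common day (57 or 180), or at last contact for subjects who leave early.
4. Order events before censorings at ties, and read Kaplan-Meier at that common day.

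The estimate then equals the crude rate when nobody is lost. At s = 10% with detection dating and the cap: 0.721 × (1 - 0.0430) = 0.690 and 0.523 × (1 - 0.1013) = 0.470. The cap is essential. Censoring at day 57 without capping or re-dating events would make the curve drop to zero if a failure is found on days 58 to 60.

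The cost is a small derivation change. Onset dates may rest on recall or be missing for some failures; the fallback in step 1 covers those. A success seen early in the window is credited with a few unobserved days (up to three at week 8), as the crude success rate already does.
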